#### **2.3.4.1 Analysis of primary efficacy endpoint(s)**

##### **2.3.4.1.1 Statistical Hypotheses**

The statistical hypothesis for the primary endpoint of 3-point MACE is to test that efpeglenatide is noninferior (1.8 and 1.3 margin) to placebo at the two-sided 5% alpha level:

- H0: Hazard ratio of efpeglenatide (pooled 4mg and 6mg groups) versus placebo  $\geq 1.8$  vs.  
Ha: Hazard ratio of efpeglenatide versus placebo  $< 1.8$

and

- H0: Hazard ratio of efpeglenatide (pooled 4mg and 6mg groups) versus placebo  $\geq 1.3$  vs.  
Ha: Hazard ratio of efpeglenatide versus placebo  $< 1.3$

The time to the first occurrence of the composite 3-point MACE endpoint (CV death, non-fatal MI, non-fatal stroke) will be analyzed using a Cox proportional hazards model with treatment (efpeglenatide 4 mg, efpeglenatide 6 mg, placebo), region (Norther America, Latin America, Europe, other), and randomization stratum of use of an SGLT2 inhibitor (current use, potential future use, neither current nor potential future use) as the factors. The analyses will be performed by including only events positively adjudicated by the CEC. Participants who receive either 4 mg or 6 mg of efpeglenatide will be combined as one efpeglenatide treatment group when making comparisons using appropriate contrast for the purposes of the primary analysis. The hazard ratio between pooled efpeglenatide and placebo will be estimated along with the associated 2-sided 95% CI. The NI with the 1.8 and 1.3 margin will be demonstrated on the primary endpoint if the upper bound of the 2-sided 95% CI is less than 1.8 and 1.3, respectively.

The time to event will be calculated as date of event as determined by the CEC (or date of censoring) – randomization date +1.

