#### Assessment of missing data

For patients who discontinued study but no MACE event was positively adjudicated by scheduled study closeout visit, the missing data are events that may occur after a patient is censored (the later of the patient's study discontinuation date and the last date they have information on CV efficacy endpoint for patients who discontinued the study).

[figure not shown]
Reasons for censoring (including non-CV death, completed study, and study discontinuation reasons) will be summarized. For patients who discontinued the study, the time from censoring date to planned study close-out visit date will be summarized to show the magnitude of missing information.

Subjects prematurely and permanently discontinuing IMP, for other reason than death, prior to study end could have a different event and hazard rate from those who stay on IMP throughout the study, and their corresponding dropout could be considered informative. This subgroup can be divided into subjects with information and subjects with missing information regarding primary MACE endpoints, see figure below.

Diagram showing subjects divided into subgroups related to missing information about MACE.

Subjects with information related to the MACE endpoint events (either discontinued study but have MACE prior to scheduled study closeout visit, or completed the study) will be used to impute data in subjects without MACE endpoints (discontinued study and no MACE event reported through third party data by scheduled study closeout visit). Subjects who developed MACE prior to the IMP discontinuation are included for imputation and their time to MACE data will be used for the imputation modeling. With these subjects included, the model estimate of hazard should fully reflect the potential hazard of the subjects with missing outcome. More specifically, subjects from below scenarios 2 and 3 will be used to impute the missing data of scenario 4 of the same treatment arm:

Note:

1. SCV: study close-out visit;
2. MACE censoring date of scenario 4 is the later of study discontinuation date or latest date with CV event information collected

The following supportive analyses will be performed to evaluate how the primary efficacy results could be influenced by different assumptions about the missing data. In particular, a 4-step approach will be used:

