- Step 1: For each arm, the hazard rate after treatment discontinuation will be generated from the posterior distribution of the parameters in the exponential survival function in subjects who have discontinued treatment but either have MACE event prior to scheduled study closeout visit or have completed study.

Note: the Kaplan-Meier curve based on observed pooled data is nearly a straight line, so constant hazard rate is assumed. So exponential survival function is used for hazard rate for each arm.

- Step 2: The missing event date of scenario 4 will be imputed multiple times by the samples of the hazard rate generated in Step 1. The imputed event date will be censored by the planned study close-out visit date if the imputed event date is after the study close out visit date.

- Step 3: In each imputation, the imputed dataset will be analyzed by the same Cox proportional hazards model as the primary analysis.
- Step 4: The results of the above analyses will be combined using Rubin's formula
- A tipping point analysis will be performed, where time to events will be imputed by using the same multiple imputation method as described above (step 1-4) and vary the hazard rates for subjects not complete study and have missing MACE event. The goal of the analysis is to find the scenarios where the result from the primary endpoints analyses will be “tipped”, i.e., the conclusion of non-inferiority will change. More specifically, a grid-search with hazard rates for the efpeglenatide group increased by an increment (e.g. 1, 1.1, 1.2, 1.3, 1.4, 1.5, 1.6, ...) will be implemented to explore the plausibility of missing data assumptions. A proper range of the hazard rates will be searched to estimate the point where the upper bound of 95% CI for the hazard ratio exceeds 1.3, and 1.8 respectively, when the corresponding comparison fails to declare statistical significance for non-inferiority.

SAS pseudo-codes is provided in [Appendix D](#).

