## Appendix D    Sample SAS® code for supportive analyses for missing data of primary efficacy endpoint

```
* VARIABLES;
* cnsrn - censoring indicator, cnsrn=1-cnsr with 1=event, 0=censor;
* adt - event or censoring date;
* rfstdt – randomization date
* EOSSTT – whether patients completed or discontinued from study;
* EOTSTT – whether patients either completed or discontinued from treatment;
* TRTEDT – treatment end date;* armn – treatment arm, 0 for control;
* planned_closeout_date – planned closeout visit date for patients without closeout visit

data sce1 sce2 sce3 sce4;
  set &data;
  aval_trted= adt-trtedt+1 ;

  ** subjects are treatment completer**;
  if EOTSTT ^= 'DISCONTINUED' THEN output sce1;
  *** 2a: subjects with MACE before IMP discontinuation; 2b:
  subjects with first MACE after IMP disct and study completer ***;
  if (EOTSTT='DISCONTINUED' and CNSRN=1 and ADT<=TRTEDT ) OR
  (EOTSTT='DISCONTINUED' and CNSRN=1 AND ADT>=TRTEDT and
  EOSSTT^="DISCONTINUED") then output sce2;
  *** subjects discontinued IMP and study, 3a: first MACE after
  pEOS, 3b: first MACE after pEOS ***/;
  if EOTSTT='DISCONTINUED' AND EOSSTT = 'DISCONTINUED' AND CNSRN=1
  AND ADT>=TRTEDT then output sce3;
  *** 4: subjects of discontinued treatment and study without MACE
  by study closeout visit ***;
  if EOTSTT='DISCONTINUED' AND EOSSTT='DISCONTINUED' and CNSRN=0
  THEN OUTPUT SCE4;
run;

*** combine scenario 2 and 3 to estimate hazard rate **;
data pattern1;
  set sce2 sce3;
run;

proc sort data=pattern1;
  by armn;
run;

ods output PosteriorSample = PostSamp;
proc phreg data = pattern1;
  model aval_trted*cnsrn(0)=;
  ** Number of imputation times = nmc/thinning = 100 times;
  bayes seed=14828 piecewise=hazard (ninterval=1 prior=gamma)
  nbi =2000 thinning=10 nmc=1000;
  by armn;
```

```
run;

/*proc print data=postsamp;
run; */

proc sort data=postsamp;
  by armn;
run;

data parout;
  retain _imput_ ;
  set PostSamp;
  by armn;

  if first.armn then
    _imput_=0;
    _imput_= _imput_ +1;
run;

DATA PATTERN2;
  SET SCE4;
RUN;

proc sort data=PATTERN2;
  by armn;
run;

proc sql;
  create table pattern2_a as
  select *
    from pattern2 as r full join parout as l
      on r.armn=l.armn;
quit;
*****;
data tempdata;
  set pattern2_a;
  by armn;
  *** Note: Simulate time to event. As a sensitivity analysis,
  multiply hazard (lambda) for treated subjects by the delta1 ***;

  if armn=1 then
    _lbdcur=Lambda1*1;
  else _lbdcur=Lambda1*&delta1;

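### The missing-data imputation counts MACE that preceded IMP discontinuation in a hazard defined as post-discontinuation, without saying how their time at risk is handled

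*SAP*

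**What the plan says.** SAP 2.3.4.1.3, Assessment of missing data, uses participants who stopped IMP and whose MACE status is known (scenarios 2 and 3) to impute event times for those who stopped IMP, left the study and had no MACE (scenario 4), within arm.

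- On participants with an earlier MACE: "Subjects who developed MACE prior to the IMP discontinuation are included for imputation", and their times to MACE enter the imputation model. The reason given is that "With these subjects included, the model estimate of hazard should fully reflect the potential hazard of the subjects with missing outcome".
- Step 1 says that "the hazard rate after treatment discontinuation will be generated from the posterior distribution of the parameters in the exponential survival function", fitted in those who "discontinued treatment but either have MACE event prior to scheduled study closeout visit or have completed study".
- The tipping-point analysis repeats these steps while multiplying the efpeglenatide hazard by 1, 1.1, 1.2 and so on.

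The text of this section gives no time origin. For the primary analysis, SAP 2.3.4.1.1 defines time to event as "date of event as determined by the CEC (or date of censoring) – randomization date +1". Appendix D instead computes "aval_trted= adt-trtedt+1", that is, from the treatment end date. It places MACE on or before that date in scenario 2a and also draws the imputed dates forward from treatment end.

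Two other rules determine who the earlier-MACE donors are. Participants stay on IMP after a cardiovascular outcome (protocol 4.1), so a non-fatal MACE can precede an IMP stop. A death on treatment counts as treatment completion (SAP 2.2), so fatal MACE on IMP do not enter the donor set.

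**The concern.** Everyone in scenario 4 was MACE-free at IMP stop. The relevant hazard is therefore that of a first MACE after stopping, among people who had none before. A donor whose first MACE came earlier was never at risk of that event. Such a donor adds one event to the numerator and no valid time to the denominator.

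Two outputs depend on this hazard: the imputed hazard ratio, and the multiplier at which non-inferiority is reported to tip. If the base is inflated by different factors in the two arms, both start from the wrong place, and a stated multiplier no longer measures the departure that it appears to measure.

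**Working it through.** **1. The plan's own figures.** From SAP 1.3, with add-on SGLT2 inhibitor use counted in full:

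- Placebo: 0.70 × 4.4 + 0.30 × 3.7 = 4.19 per 100 patient-years (PY).
- Efpeglenatide: 0.75 × 4.4 × 0.85 + 0.25 × 3.7 = 3.73 per 100 PY.
- Hazard ratio (HR) 3.73/4.19 = 0.890.
- Power with 330 events and 2:1 pooled allocation: Φ(√(330 × 2/9) × ln(1.3/0.890) − 1.96) = 90%, and above 99% at 1.8. Both stated figures are reproduced.

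**2. Form of the error.** Let a be donor MACE before IMP stop, b donor MACE after it, and T the post-stop time. The hazard wanted is b/T. If the earlier events are counted over post-stop time, the estimate is (a + b)/T, so

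inflation = 1 + a/b.

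With IMP stop at 6% per year and no MACE leading to a stop, the placebo arm has about 9 post-stop MACE and about 17 donor MACE in all: 17/9 = 1.9. With 20% of non-fatal MACE leading to a stop, about two thirds of donor MACE are pre-stop: 1/(1 − 2/3) = 3.

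**3. Size by simulation.** From the documents: the rates above, 2% per year study leaving, 24 to 36 months of follow-up. Assumed, because the documents do not give them: IMP stop 6% per year, 35% of MACE fatal, 0 to 30% of non-fatal MACE leading to an IMP stop. The placebo post-stop hazard is about 4.2 per 100 PY. The donor set in the SAP text, over post-stop time, gives 7.9 to 16.8, or 1.9 to 4.0 times too high.

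**4. Other readings and assumptions.** A second simulation (4.2% per year) varied stop timing from early to very late and took 70% or 100% of MACE as non-fatal:

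| Treatment of earlier-MACE donors | No MACE-led stopping | 20% MACE-led stopping |
|---|---|---|
| Events, time at risk only after IMP stop | 1.3 to 5.1 | 2.0 to 9.1 |
| All donors timed from randomization | 0.9 to 1.2 | 1.3 to 2.5 |
| Earlier-MACE donors left out | 1.00 to 1.03 | 1.00 to 1.03 |

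Under the 6% per year assumptions of step 3, the randomization clock gives about 1 to 2.

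**5. Difference between arms.** The true hazard ratio in these runs is about 0.89. With IMP stop at 6% per year on placebo and 9% on efpeglenatide, the ratio of imputed hazards falls to between 0.85 and 0.70 as MACE-led stopping rises from 0 to 30%. With the stop rates reversed it is about 1.00 to 1.13. At a base ratio of 0.73 (20% MACE-led stopping), a tipping multiplier of 0.89/0.73 = 1.22 does no more than undo the bias.

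**6. Effect on the imputed result.** With 4000 participants and 2% per year leaving, about 62 placebo and 124 efpeglenatide participants are imputed, over about 240 missing person-years. The upper bounds are approximate and treat imputed events as observed.

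| Inflation, placebo / efpeglenatide | Imputed events | HR (upper bound), true HR 0.890 | HR (upper bound), true HR 1.05 |
|---|---|---|---|
| 1 / 1 | 9.1 | 0.890 (1.101) | 1.050 (1.291) |
| 2 / 2 | 17.5 | 0.890 (1.099) | 1.050 (1.288) |
| 4 / 4 | 32.9 | 0.891 (1.095) | 1.050 (1.283) |
| 4 / 1.4 | 19.7 | 0.843 (1.038) | 0.994 (1.217) |
| 2 / 4 | 27.5 | 0.928 (1.143) | 1.093 (1.340) |

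Imputed events are for the planning HR of 0.890. The last two rows are deliberately unequal. With the 6% and 9% stop rates of step 5, the HR moves only from about 0.884 to 0.872–0.874, and the upper bound from about 1.09 to 1.07–1.08.

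**The case against.** **The text does not fix the clock.** The post-stop clock appears only in Appendix D, which is labelled sample code. If time to MACE means time from randomization, as in the primary analysis, there is little inflation unless MACE itself leads to stopping. If non-positive times are discarded, there is none. The section's scenario figure, not shown in the text available, may state the origin. This stands: a reader might infer that the SAP necessarily inflates the hazard 2- to 4-fold, and the documents do not support a single factor. The rule still needs correcting. The randomization clock mixes on-IMP time into a hazard that the section wants separate from it, and Appendix D imputes forward from IMP stop. Discarding the records means that the stated inclusion is not carried out.

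**Direction.** A reader might infer a bias in favour of efpeglenatide. Protocol 2.3 reports dose-dependent discontinuation in earlier studies, which makes earlier stopping on efpeglenatide plausible. Neither document gives IMP-stop rates or timing by arm, and the reverse pattern biases against efpeglenatide.

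**Robustness.** With equal inflation the HR does not move, and each multiplier step adds more efpeglenatide events, so the result tips sooner. That is conservative for non-inferiority. It is correct, but it does not cover unequal inflation.

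**The code as drafted departs from the text.** Its scenarios 2 and 3 keep only participants with an event, so IMP discontinuers who completed the study without MACE enter no scenario. That is a separate and larger error. The figures here use the donor set in the text, so they do not describe the code's output as drafted. Repairing that error leaves the present rule in place.

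**Conclusion.** The donor set, the name of the estimate and the clock do not agree, and the stated rule does not estimate the hazard that scenario 4 needs. If earlier MACE count over post-stop time, the factor is about 1.9 to 4.0 under 6% per year IMP stop and 0 to 30% MACE-led stopping, and about 1.3 to 9 over wider assumptions. On the randomization clock it is about 1 to 2 under the 6% per year assumptions. All of these rest on IMP-stop inputs that the documents do not contain.

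Inflation may differ by arm in either direction: towards efpeglenatide if its participants stop IMP earlier or more often, against it if the reverse. At the planning HR the shift is modest and the upper bound stays well below 1.3. It could change the supportive conclusion only near the margin, as in the 1.05 column. The primary analysis is untouched. The SAP should be corrected because the tipping point is reported as a measure of robustness and would start from a wrong base.

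**What to change.** In SAP 2.3.4.1.3, replace the inclusion of earlier-MACE participants with: *The Step 1 hazard model uses participants who permanently discontinued IMP and were MACE-free at IMP discontinuation. Time runs from IMP discontinuation to first positively adjudicated MACE or censoring.* Remove scenario 2a from the hazard model in the text and in Appendix D. Keep those participants as observed events in the Cox step.

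Adding the observed event-free post-stop time of scenario 4 is an optional refinement; leaving it out raises the estimated hazard by only about 2%.

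The change costs one sentence and one subset statement. Fewer events inform the hazard: about 9 instead of 17 on placebo in the 6% per year case, and about a third of the total if 20% of non-fatal MACE lead to a stop. The approximate relative standard error of the hazard (1/√events) rises from 1/√17 = 24% to 1/√9 = 33%, so the posterior is wider. That is the real uncertainty about the post-stop hazard, and the imputation should carry it.

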### 1.3 DETERMINATION OF SAMPLE SIZE

It is estimated that approximately 4000 participants are needed to obtain approximately 330 participants with a positively adjudicated event for the primary composite cardiovascular endpoint (3-point MACE), based on the following trial design characteristics assumptions:

[figure not shown]
- A recruitment period of approximately 12 months
- Study duration is estimated to be approximately 24 months of follow-up after the last randomized patient, estimated follow-up ranging from 24 to 36 months
- 2% annual early study discontinuation
- Yearly event rate in placebo group: 4.4% for participants not using a SGLT2 inhibitor, and 3.7% for participants using a SGLT2 inhibitor
- Treatment effect of efpeglenatide compared to placebo: 15% risk reduction for participants not using a SGLT2 inhibitor, and a neutral effect for participants using a SGLT2 inhibitor
- 20% of participants using a SGLT2 inhibitor at baseline, and additional 10% participants in placebo group and 5% participants in efpeglenatide group adding a SGLT2 inhibitor during the study period

This will provide:

- 90% power to demonstrate non-inferiority (NI) of efpeglenatide vs placebo with a 1.3 NI margin {upper bound of the 95% CI of the estimated hazard ratio <1.3} for the 3-point MACE (CV death, non-fatal MI or non-fatal stroke)
- >99% power to demonstrate NI with a 1.8 margin

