#### ***a. General censoring rule for primary MACE efficacy endpoint:***

For patients who have no primary MACE endpoints, they will be censored using the following rules:

- Patients who completed the study and not died before the study completion will be censored at their study close-out visit date or follow-up visit date.

Note: If there are CV events happening after the patient's study close-out visit date and the event's proceeding/related event's onset date is on or before the study close-out visit date, in this case, this CV events will be included in efficacy analysis if it positively adjudicated. The patient will still be censored at study close-out visit date if these events not adjudicated positively.

For example, for a CV death, if the onset date of its proceeding fatal stoke is before the patient's study close-out visit date and the CV death date is after study close-out visit date (before DBL date), this CV death will be included in efficacy analysis if positively adjudicated as CV death.

Another example, for a HHF, if the onset date of its proceeding HF is before study close-out visit date and its resulted hospitalization is after study close-out visit date, this HHF will be included in efficacy analysis if positively adjudicated. Otherwise, the patient will be censored at study close-out visit date if the HHF is not positively adjudicated.

- Patients who died before study close-out (i.e. Death reported on the 'Completion of End of Study') will be censored at their date of Non-CV death
- Patients who discontinued the study will be censored at their later of study discontinuation date or latest date with cardiovascular efficacy endpoint information (MI/UA, heart failure,

cerebrovascular event, coronary procedure, admission to hospital/emergency room, or cardiac biomarkers as collected in eCRF) collected.

More specific: If there are events happening after the patient's study discontinuation date and the events are not positively adjudicated, the latest date of these events will be the new censored date of the patient.

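### Step 1 of the missing-data analysis uses study leavers as donors only if they had a MACE, so the imputation hazard is biased upward and the tipping-point multiplier is distorted

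*SAP*

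**What the plan says.** The SAP sorts participants who stopped IMP early into scenarios. From the text and the Appendix D comments (the diagram is not reproduced):

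- Scenario 2: MACE before IMP stop, or stayed in the study to completion.
- Scenario 3: left the study and had a MACE.
- Scenario 4: left the study with no MACE by scheduled close-out.

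The donor rule is that "subjects from below scenarios 2 and 3 will be used to impute the missing data of scenario 4 of the same treatment arm". Step 1 repeats it: the exponential hazard is estimated "in subjects who have discontinued treatment but either have MACE event prior to scheduled study closeout visit or have completed study".

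Scenario 4 does have observed time. A note in the same section dates its censoring at study discontinuation or at the last CV event information, whichever is later. Appendix C adds that for events after discontinuation that are not positively adjudicated, "the latest date of these events will be the new censored date of the patient".

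Step 2 draws event dates from the Step 1 hazard, and its only stated limit is this: "The imputed event date will be censored by the planned study close-out visit date". The tipping-point analysis then multiplies the efpeglenatide hazard over a grid and leaves the placebo hazard at its Step 1 value. The constant hazard is justified by the statement that "the Kaplan-Meier curve based on observed pooled data is nearly a straight line, so constant hazard rate is assumed".

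**The concern.** An exponential hazard is events divided by time at risk. Among leavers, events enter the numerator through scenario 3, while the event-free time of scenario 4 never enters the denominator. That is selection of donors on the outcome being modelled. The SAP treats the dropped time as known: Appendix D uses it to condition each imputed date on survival to the censoring date. It is thus used in drawing the imputations but not in estimating the hazard they are drawn from.

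The other sensitivity analyses in 2.3.4.1.3 impute nothing. This is the plan's only imputation and tipping-point examination of whether missing follow-up could overturn non-inferiority, and its output is a multiple of the Step 1 hazard.

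Step 2 has a smaller gap. Sites seek vital status after study discontinuation (SAP 2.1), but nothing stops a MACE being imputed after a known non-CV death.

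**Working it through.** **Plan's own figure.** SAP 1.3 states "90% power to demonstrate non-inferiority (NI) of efpeglenatide vs placebo with a 1.3 NI margin" and that "approximately 4000 participants are needed to obtain approximately 330" events; 2.3.4.1.1 sets the test as "noninferior (1.8 and 1.3 margin) to placebo at the two-sided 5% alpha level". Rates with the SAP's SGLT2 inhibitor mix:

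- placebo 0.70×4.4 + 0.30×3.7 = 4.19%/yr
- efpeglenatide 0.75×(0.85×4.4) + 0.25×3.7 = 3.73%/yr
- HR = 3.73/4.19 = 0.890

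With 2:1 allocation, ln(1.3/0.890)×√(330×2/9) − 1.96 = 1.28, which is 90% power. The design reproduces. The documents give no figure for the imputation hazard or the multiplier.

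**Hazard inflation.** Let D be post-stop MACE, T the observed post-stop time of all IMP discontinuers, and T4 the part belonging to scenario 4. The full-data estimate is D/T and Step 1 gives D/(T − T4). The inflation is T/(T − T4) = 1/(1 − f), with f = T4/T. It is 1 only if f = 0.

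Assumptions, none from the documents except follow-up: constant MACE hazard 0.0388/yr, follow-up uniform on 2-3 years, IMP stop 5-10%/yr, exponential lag from IMP stop to study exit, no third-party events, post-stop MACE only. Simulated inflation:

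| Share of discontinuers leaving | Exit on day of IMP stop | Mean lag 0.25-1 yr |
|---|---|---|
| 20% | 1.00 | 1.04-1.07 |
| 40% | 1.00 | 1.10-1.16 |
| 60% | 1.00 | 1.23-1.33 |

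Example (40% leaving, lag 0.5 yr, IMP stop 10%/yr): 0.0443/yr as written against 0.0384/yr with scenario 4 included, a ratio of 1.15, so f = 1 − 1/1.15 = 13%. Adding scenario 4 as right-censored restores the hazard. Inflation hardly changes between IMP stop rates of 5% and 10%/yr; the share leaving and the lag drive it.

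**Tipping multiplier at margin 1.3.** This is an expected-count approximation that ignores between-imputation variance. Inputs: 330 observed events, 5% leavers (133.3 efpeglenatide, 66.7 placebo), missing time uniform on 0.1-2.5 years, true hazards 0.0373 and 0.0419/yr. With a and b the observed plus imputed events on efpeglenatide and placebo, the result tips when ln(a/2b) + 1.96√(1/a + 1/b) = ln 1.3.

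Check at observed HR 1.0 with no inflation: b = 110 + 3.5 = 113.5. A multiplier of 2.67 gives a = 220 + 15.9 = 235.9. Then 0.038 + 0.224 = 0.262 = ln 1.30.

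| Inflation (efpeglenatide, placebo) | HR 0.89 | HR 1.0 |
|---|---|---|
| none | 9.02 | 2.67 |
| 1.06, 1.06 | 8.63 | 2.60 |
| 1.15, 1.15 | 8.12 | 2.51 |
| 1.33, 1.33 | 7.31 | 2.37 |
| 1.06, 1.33 | 9.17 | 2.97 |

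Equal inflation lowers the multiplier by 4-19% at HR 0.89 and 3-11% at HR 1.0. A proportional effect would be 1 − 1/1.06 = 6% to 1 − 1/1.33 = 25%. With efpeglenatide at 1.06, the multiplier is overstated once placebo inflation passes about 1.26 (HR 0.89) or 1.11 (HR 1.0).

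**Pooled HR without a multiplier, observed HR 1.0.** With no inflation: 226.3/(2×113.5) = 0.997. With 1.33 in both arms: 228.3/(2×114.6) = 0.996. With 1.06 and 1.33: 226.6/(2×114.6) = 0.989. All changes are under 1%.

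**Third-party events.** If half of MACE after study exit are captured, Step 1 inflation is 1.12-1.81. Adding scenario 4 time alone then leaves 0.041-0.066/yr against 0.038, because events after exit count without matching event-free time.

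**The case against.** The strongest reply is that this is a supportive analysis, that it changes few imputed events against about 330 observed, and that a hazard inflated in both arms makes non-inferiority look more fragile, so the error is conservative. The first two parts stand, and they limit the weight of the point. The third holds only if the arms are inflated about equally. Protocol 2.3 reports that discontinuations appeared dose dependent in earlier studies, so different mixes of stayers and leavers by arm are plausible, and the direction cannot be known in advance.

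A second reply is that the size rests on assumptions. That is correct. If every leaver exits on the day IMP stops, there is no bias.

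A reader might infer that the multiplier is always too small, or falls in proportion to the hazard inflation. The documents do not support that. Step 1 is applied to each arm, so the placebo hazard is inflated too, and only efpeglenatide is multiplied.

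A reader might also infer that the constant-hazard note is wrong. It does not say whose data were pooled or from which time origin, so it supports a request for a check and no more.

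On death after study exit, Appendix C does not list death among its sources of CV information, so the censoring date of such a participant is unclear. Step 2 sets no limit at death either way.

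**Conclusion.** The donor rule in Step 1 is wrong as written. It selects study leavers on outcome and biases the hazard upward whenever they are observed after stopping IMP. The factor is 1/(1 − f), about 1.04 to 1.33 under the lagged-exit assumptions shown. The real value depends on the share leaving and the lag, which the plan does not state.

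The tipping-point multiplier is distorted in a direction that depends on the relative inflation of the two arms, so it cannot be read as either conservative or anti-conservative. The primary analysis and its non-inferiority decision are not affected.

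The figures count post-stop MACE only, which isolates this rule from the SAP's inclusion of donors whose MACE preceded IMP stop. They also describe the SAP text. The Appendix D code departs from that text: both donor data sets require an event, so off-IMP completers without a MACE drop out of the hazard fit and of the stacked data for the Step 3 Cox model. That is a separate and larger fault, and correcting the code to match the text would leave the present one in place.

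The missing limit at non-CV death is a small gap whose size was not estimated. The point merits a correction before database lock.

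**What to change.** - **Step 1:** fit the hazard to all IMP discontinuers (scenarios 2, 3 and 4) on time since IMP stop, with scenario 4 right-censored at the MACE censoring date.
- **Third-party data:** count events and event-free time over the same period. Either censor all leavers at study exit for the hazard fit, including those with a later third-party event, or use third-party event-free follow-up where it exists.
- **Appendix D:** make the donor selection and the stacked analysis data match the revised Step 1, including off-IMP completers without a MACE.
- **Step 2:** impute no MACE beyond the date of a known non-CV death.
- **Optional:** check the constant hazard in IMP discontinuers on time since IMP stop.

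The cost is a few sentences and a few lines of code. No new data are needed.
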